2 LIST OF ABBREVIATIONS AND DEFINITIONS OF TERMS

Abbreviation	Term
AE	adverse event
AUC(0-inf)	area under the concentration-time curve from zero time extrapolated to infinite time
AUC(0-t)	area under the concentration-time curve from zero time to time of last quantifiable concentration
BLQ	below the limit of quantification
CCR4	CC chemokine receptor 4
CI	confidence interval
CL	total clearance
CR	complete response
CRF	case report form
CTCAE	common terminology criteria for adverse events
CTCL	cutaneous T-cell lymphoma
CV	coefficient of variation
C _{max}	maximum observed concentration
DOR	duration of response
ECG	electrocardiogram
ECOG	Eastern Cooperative Oncology Group
FAS	full analysis set
IC	informed consent
IL-2	interleukin-2
LDH	lactate dehydrogenase
LLOQ	lower limit of quantification
MedDRA	medical dictionary for regulatory activities
ORR	objective response rate
OS	overall survival
PD	Pharmacodynamics
PD	progression disease

PFS	progression-free survival
РК	Pharmacokinetic
PS	performance status
РТ	preferred term
PTCL	peripheral T-cell lymphoma
QT	ECG interval from the beginning of the Q wave to the end of the Twave
QTc	QT interval corrected for heart rate
R _{2adj}	adjusted regression coefficient
R _{ac}	accumulation index
SD	Standard deviation
SOC	system organ class
TEAE	treatment-emergent adverse event
TEMAV	treatment-emergent markedly abnormal laboratory value
TTR	time to response
V _{ss}	volume of distribution at steady state
Vz	volume of distribution at terminal phase
WHO DD	World Health Organization Drug Dictionary
sIL-2R	soluble interleukin-2 receptor
t _{1/2}	terminal elimination phase half-life
t _{max}	time at which the highest drug concentration occurs
λ_z	terminal phase rate constant

3 INTRODUCTION

The purpose of this statistical analysis plan is to describe the procedures and the statistical methods and pharmacokinetics (PK) analysis methods that will be used to analyze and report results for Eisai Protocol E7777-J081-205.

3.1 Study Objectives

3.1.1 Primary Objective

To evaluate the efficacy (objective response rate: ORR) of E7777 in patients with relapsed or refractory peripheral T-cell lymphoma (PTCL) and cutaneous T-cell lymphoma (CTCL).

3.1.2 Secondary Objectives

- (1)To evaluate the efficacy of E7777 below.
 - · Progression-free survival (PFS)
 - · Duration of response (DOR)
 - Time to response (TTR)
 - · Complete response (CR) rate
 - ·Overall survival (OS)
- (2)To evaluate the safety of E7777.
- (3)To evaluate the PK and immunogenicity (anti-E7777 antibody, anti- interleukin-2 (IL-2) antibody and neutralizing activity of anti-E7777 antibody) of E7777.

3.1.3 Exploratory Objectives

To preliminarily explore the biomarkers of tumor and the blood below.

- (1)To measure the rate of CD25+ cells in tumor by immunohistochemistry.
- (2)To measure the amount of serum soluble IL-2 receptor (sIL-2R) and lactate dehydrogenase (LDH).
- (3)To measure the T-cell subsets in the peripheral blood.

3.2 Overall Study Design and Plan

This is a multicenter, single-arm, open label, Phase 2 to evaluate efficacy, safety, PK and immunogenicity of E7777 in patients with relapsed or refractory PTCL and CTCL. This study composed of the following 3 periods: preparation, treatment and follow-up periods. The preparation period consists of the following four procedures: informed consent (IC), screening, enrollment, and baseline assessment. Informed consent (IC) is able to obtain 28 days before the treatment. Enroll the patient who meet the inclusion criteria and does not meet the exclusion criteria. Conduct the baseline assessment within 7 days before the treatment. Confirm that the patient continue to meet the inclusion criteria and does not meet the exclusion criteria before moving to the treatment period. The

treatment period consists of 1 cycle of 3 weeks and lasts until meet the "discontinuation criteria" or Day 21 of Cycle 8. The evaluation at discontinuation will be performed within 7 days after termination of study treatment.

4 DETERMINATION OF SAMPLE SIZE

Thirty-five patients were required to detect lower limit of the 95% confidence interval (CI) that exceed the 5% threshold in ORR, which is the primary endpoint of the study, with the expected ORR is 25% with a statistical power of 90%. In CTCL, 6 or more patient is targeted to evaluate the safety as specific disease.

5 STATISTICAL METHODS

All descriptive statistics for continuous variables will be reported using mean, standard deviation (SD), median, minimum and maximum. Categorical variables will be summarized as number (percentage) of subjects.

5.1 Study Endpoints

5.1.1 Primary Endpoint

Objective response rate (ORR) of best overall response

5.1.2 Secondary Endpoints

- Progression-free survival (PFS)
- Duration of response (DOR)
- Time to response (TTR)
- Complete response (CR) rate
- Overall survival (OS)
- Safety endpoints (adverse events [AEs], clinical laboratory parameters, vital signs, weight, Eastern Cooperative Oncology Group [ECOG] performance status [PS], 12-lead electrocardiograms [ECGs] results, and ophthalmologic test results)
- Pharmacokinetic (PK) parameters
- Immunogenicity (anti-E7777 antibody, anti-IL-2 antibody and neutralizing activity of anti-E7777 antibody)

5.1.3 Exploratory Endpoints

Biomarkers of tumor (CD25+, CC chemokine receptor 4 [CCR4] expression) and following Pharmacodynamics (PD) biomarkers from the blood.

• sIL-2R, LDH

• T-cell subsets (CD4+, CD4+/CD25+, CD4+/CD25+/Foxp3+, *CD4+/CD7-, *CD4+/CD26-)(*Only for mycosis fungoides and Sézary syndrome)

5.2 Study Subjects

5.2.1 Definitions of Analysis Sets

Full Analysis Set (FAS):

Defined as a group of subjects who have received at least one dose of the study drug. This group will be the population for the evaluation of efficacy.

Safety Analysis Set:

Defined as a group of subjects who have received at least one dose of the study drug with at least one evaluable post-baseline safety data. This group will be the population for the evaluation of safety.

Pharmacokinetics Analysis Set:

Defined as a group of subjects in who have received at least one dose of the study drug with at least one serum concentration data.

Pharmacodynamics Analysis Set:

Defined as a group of subjects in who have received at least one dose of the study drug with at least one evaluable pre and post-baseline PD data.

On eligibility-confirmed subjects, the number (percentage) of subjects included in each analysis set will be summarized.

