5.2.2 Subject Disposition

The number (and percentage as needed) of subjects signed IC, continued in the study after screening and screen failures will be provided and primary reasons for screening failure will be summarized for all subjects. The number and percentage of subjects treated, untreated, completed the study, discontinued the study and the primary reasons for study discontinuation will be summarized for each disease (PTCL, CTCL, Other, as appropriate, determined by central review) and overall.

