5.3 Data Analysis General Considerations

All efficacy analyses will be conducted based on FAS.

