5.3.4 Examination of Subgroups

All efficacy analyses will be conducted for each disease and overall.

Primary efficacy analysis based on the independent assessment results will be performed by the following subgroups: sex (Male/ Female) and age group (<65, >=65), ECOG PS (0/1), Baseline CCR4 Status (Postive/ Negative), CD25+ Cell Rate (category1: <1%, 1-<10%, 10-<20%, 20-<50%, >=50, category2: <20%, >=20%), Relapsed/ Refractory status, previous systemic chemotherapy regimen (<=2, >2) and prior use of newly approved agent (Yes/ No).

Analysis of TEAEs by SOC and PT will be performed by the following subgroups: sex, age group and ECOG PS.

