5.4 Efficacy Analyses

FAS will be the primary analysis population. All efficacy result will be summarized for each disease and overall. Results from central assessment by efficacy and safety evaluation committee and investigator assessment will be used, as applicable. If needed, efficacy analysis results per investigator assessment will also be summarized. Unless otherwise noted, overall response considering both "Revised Response Criteria for Malignant Lymphoma (Cheson, J Clin Oncol; 2007)" and "Clinical Endpoints and Response Criteria in Mycosis Fungoides and Sézary Syndrome (Olsen, J Clin Oncol; 2011)" will be used.

For summarization of tumor assessment relevant analysis except PFS and DOR, assessment results until discontinuation from study treatment will be used.

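### Does counting dosed subjects classed as Other in the overall ORR, with no pooled PTCL+CTCL line, undermine the comparison with 5%?

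*SAP*

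**What the plan says.** The primary objective (SAP 3.1.1) concerns ORR "in patients with relapsed or refractory peripheral T-cell lymphoma (PTCL) and cutaneous T-cell lymphoma (CTCL").

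Section 4 sizes the trial at 35 patients. The aim is a "lower limit of the 95% confidence interval (CI) that exceed the 5% threshold in ORR, which is the primary endpoint of the study". The calculation assumes a true rate of 25% and claims 90% power.

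Section 5.2.1 defines the FAS by receipt of at least one dose, with no condition on confirmed diagnosis: "This group will be the population for the evaluation of efficacy". Section 5.3 repeats this: "All efficacy analyses will be conducted based on FAS".

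The category Other appears once, in the disposition section (5.2.2), where counts are given "for each disease (PTCL, CTCL, Other, as appropriate, determined by central review) and overall".

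For efficacy, section 5.3.4 says "All efficacy analyses will be conducted for each disease and overall" and section 5.4 says "All efficacy result will be summarized for each disease and overall". Section 5.4.1 gives ORR with an exact 95% interval and makes the central assessment primary. It adds ORR under the disease-specific criteria for PTCL and for CTCL separately. Section 5.4.3 adds ORR by histology.

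**The concern.** Read together, these sections seem to leave a mismatch. The objective names two diseases, the efficacy population is everyone dosed, and the SAP itself foresees a third class after central review. A dosed subject in that class enters the numerator and denominator of the ORR compared with 5%. No planned line gives the ORR and exact interval for PTCL and CTCL together without Other.

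The verdict against 5% would be at stake. With about 35 patients a single responder can move the exact lower limit across the threshold. An Other subject might then decide a conclusion stated for PTCL and CTCL, and an interval for those two diseases computed after seeing the data could be called post hoc.

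**Working it through.** **Inputs.** From the SAP: n = 35, threshold 5%, expected ORR 25%, power 90% (section 4); exact 95% interval (5.4.1), taken as two-sided Clopper-Pearson. Not in the SAP: the number k of dosed Other subjects and their response rate q. I take k = 1 or 2, and q = 25% unless stated otherwise.

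**1. The plan's own figure.** The exact lower limit for x responders of n is the 2.5% quantile of Beta(x, n − x + 1).

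- 5/35: 4.81%, fails.
- 6/35: 6.56%, passes.

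The rule is therefore 6 or more of 35. P(X ≥ 6 | n = 35, p = 0.25) = 90.2%, which reproduces the stated power. P(X ≥ 6 | n = 35, p = 0.05) = 0.7%.

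**2. Can the overall and PTCL+CTCL results disagree?** Yes, near the boundary. The smallest passing count is 5 at n = 33 and 6 at n = 34 and n = 35.

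| Case | Overall | PTCL+CTCL |
|---|---|---|
| One Other, a responder | 6/35: 6.56%, passes | 5/34: 4.95%, fails |
| Two Other, neither responds | 5/35: 4.81%, fails | 5/33: 5.11%, passes |

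**3. How often, at n = 35 and 25% response in all?**

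- k = 1, overall passes and PTCL+CTCL fails: this needs exactly 5 of 34 plus the Other subject responding. 0.0647 × 0.25 = 1.62%. The reverse cannot happen.
- k = 2, overall passes and PTCL+CTCL fails: this needs 4 of 33 plus both Other subjects responding. 0.0381 × 0.25² = 0.24%.
- k = 2, overall fails and PTCL+CTCL passes: this needs 5 of 33 plus neither Other subject responding. 0.0736 × 0.75² = 4.14%.

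If Other subjects do not respond (q = 0), the first kind of disagreement has probability 0 for k = 1 and k = 2. Keeping them in then only costs power: overall power falls from 90.2% to 88.6% (k = 1) and 86.8% (k = 2).

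**4. Is the PTCL+CTCL figure lost?** No. Sections 5.3.4 and 5.4 require the ORR by disease. Unless otherwise noted, 5.4 uses one overall response, considering both sets of criteria, for every row. The separate criteria-specific ORRs in 5.4.1 are additional. The PTCL and CTCL rows and the overall row therefore share a response definition, an assessor and the FAS. The pooled numerator and denominator are the sums of the two rows, whether or not Other is printed as a third row. The interval follows from those two integers by the method 5.4.1 already fixes.

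**5. Does the FAS contradict the objective?** No. The objective states the disease setting and the FAS states who is counted. Counting everyone treated, including those whom central review later reclassifies, guards against exclusions made after treatment has begun.

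**The case for a change.** The strongest case for the concern is that the SAP created the third category and also defines the reporting rows, so the gap cannot be left to the protocol. Responder counts can be summed, but the interval compared with 5% is not a planned output. Fixing one line in advance costs almost nothing and removes any suspicion of choosing the population once the result is known. Other subjects could also flatter the result: if the true PTCL/CTCL ORR were 5% and Other subjects responded at 25%, the chance of passing would rise from 0.7% to 1.1% (k = 1), 1.7% (k = 2) and 4.7% (k = 5).

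It is true that no pooled PTCL+CTCL line is pre-specified and that the two results can differ near the boundary. That does not amount to an error:

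- The rise in false passes stays below the nominal one-sided 2.5% for up to three such subjects (2.4% at k = 3). It exceeds it only from four of 35 (3.4% at k = 4), all assumed to respond at five times the threshold rate. Nothing in the SAP suggests such numbers.
- The primary population, assessor and interval method are fixed, so no choice is left open for the primary result.
- An added line would come with no rule for reading a disagreement with the primary, so it would not settle the borderline case.
- Other is named only for disposition, and only where appropriate. That section also counts untreated subjects, so it does not show that anyone so classed is dosed. Whether such a subject falls outside the eligible diseases depends on the protocol, which is not at hand.

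**Conclusion.** The concern does not hold. The SAP states no wrong number or rule here and does not contradict itself. Followed as written, it gives a sound primary result: ORR by central assessment in all treated subjects, with an exact interval and a design that reproduces at 6 or more of 35 and 90.2% power. The PTCL+CTCL result can be recovered from the planned disease rows without further choices. A pooled line would be a matter of preference.

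At n = 35 the chance that the overall and PTCL+CTCL results fall on different sides of 5% is 1.6% with one Other subject and 0.24% + 4.14% = 4.4% with two. In the second case the larger part comes from the all-treated set being the stricter one. These figures assume 25% response in all subjects and a Clopper-Pearson interval, and they read the 5% threshold of section 4 as applying to the overall FAS row. If no dosed subject is classed as Other, the two results are identical.

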5.2.2 Subject Disposition

The number (and percentage as needed) of subjects signed IC, continued in the study after screening and screen failures will be provided and primary reasons for screening failure will be summarized for all subjects. The number and percentage of subjects treated, untreated, completed the study, discontinued the study and the primary reasons for study discontinuation will be summarized for each disease (PTCL, CTCL, Other, as appropriate, determined by central review) and overall.

5.2.3 Demographic and Other Baseline Characteristics

Demographic and baseline characteristics for FAS and the safety analysis set (and the PK analysis set if any discrepancy) will be summarized for each disease and overall using descriptive statistics. Continuous demographic and baseline variables include Age, Height, and Weight. Categorical variables include Sex, Age group (<65, 65<=), Race, Ethnicity, ECOG PS, CCR4 Expression category, CD25+ Cell Rate category and Relapsed/Refractory status (Relapsed: BOR of CR or PR in last previous systemic chemotherapy, Refractory: BOR of SD or PD in last previous systemic chemotherapy, and Unknown). In addition, number and percentage of subjects with each disease histology and each stage will be summarized for each disease and overall.

5.2.4 Prior and Concomitant Therapy

For the FAS, the number and percentage of subjects with each prior treatment (systemic chemotherapy, systemic anti-neoplastic [except systemic chemotherapy], topical therapy, autologous stem-cell transplantation, extracorporeal therapy [except radiotherapy], radiotherapy, surgery[except biopsy]) will be provided. The number of previous systemic chemotherapy regimen will be summarized as categorical variable and continuous variable for each disease and overall. The number and percentage of subject with each previous systemic chemotherapy will be also provided for each disease and overall.

All investigator terms for medications recorded in the case report form (CRF) will be coded to an 11-digit code using the World Health Organization Drug Dictionary (WHO DD). Prior medications are defined as medications that stopped before the first dose of study drug. Concomitant medications are defined as medications that (1) started before the first dose of study drug and were continuing at the time of the first dose of study drug, or (2) started on or after the date of the first dose of study drug. Any subthequent anti-cancer therapies are not regared as concomitant but listed separately. All medications will be presented in subject data listings.

5.2.5 Treatment Compliance

For the Safety Analysis set, the number and percentage of subjects who experienced at least one dose skipping / delay of the start of the cycle / dose reduction will be provided for each cycle/all period for each disease and overall. Reasons of delay and reduction will also be summarized for each disease and overall.

5.3 Data Analysis General Considerations

All efficacy analyses will be conducted based on FAS.

5.3.1 Pooling of Centers

Subjects from all centers will be pooled for all analyses.

5.3.2 Adjustments for Covariates

No adjustment for covariates will be performed.

5.3.3 Multiple Comparisons/Multiplicity

No statistical comparison is planned in this study.

5.3.4 Examination of Subgroups

All efficacy analyses will be conducted for each disease and overall.

Primary efficacy analysis based on the independent assessment results will be performed by the following subgroups: sex (Male/ Female) and age group (<65, >=65), ECOG PS (0/1), Baseline CCR4 Status (Postive/ Negative), CD25+ Cell Rate (category1: <1%, 1-<10%, 10-<20%, 20-<50%, >=50, category2: <20%, >=20%), Relapsed/ Refractory status, previous systemic chemotherapy regimen (<=2, >2) and prior use of newly approved agent (Yes/ No).

Analysis of TEAEs by SOC and PT will be performed by the following subgroups: sex, age group and ECOG PS.

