5.4.1 Primary Efficacy Analyses

The rate of subjects whose best overall response is CR or PR is calculated as ORR, and the Exact 95% CI is also calculated. Analysis based on central assessment by Efficacy and safety evaluation committee will be regarded as primary result.

Additionally, For PTCL, best overall response and ORR using overall response evaluated according to "Revised response criteria for malignant lymphoma" will be summarized. And for CTCL, best overall response and ORR based on global response score of "Clinical end points and response criteria in mycosis fungoides and Sézary syndrome" will be summarized.

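### Tumour CD25+ rate is related to response only through ORR in five small bins and at one 20% cut; one exploratory estimate on the recorded rate would keep information that the bins discard

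*SAP*

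**What the plan says.** SAP 3.1.3 lists CD25 first among the exploratory objectives: "To measure the rate of CD25+ cells in tumor by immunohistochemistry". SAP 5.1.3 repeats tumour CD25+ as an exploratory endpoint.

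The link to response is in SAP 5.3.4: "Primary efficacy analysis based on the independent assessment results will be performed by the following subgroups". One of the factors is "CD25+ Cell Rate (category1: <1%, 1-<10%, 10-<20%, 20-<50%, >=50, category2: <20%, >=20" percent. By SAP 5.4.1 the quantity reported in each subgroup is ORR, for which "the Exact 95% CI is also calculated".

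The only other specified use of tumour CD25 is SAP 5.2.3, where it is a categorical baseline variable; the continuous baseline variables are age, height and weight. The pharmacodynamics part of SAP 5.5.2 summarises measured values of sIL-2R, LDH and T-cell subsets, but not tumour CD25. SAP 5.3.3 plans no statistical comparison. SAP 5.7 leaves room for further exploratory analyses without naming any.

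**The concern.** The objective speaks of a rate, yet every specified use turns it into a category. Two things are lost:

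- **Position within a bin.** At the 20% cut, a tumour with 21% positive cells counts the same as one with 95%. The five-bin version does separate 20 to under 50% from 50% and above.
- **Order of the bins.** The five ORRs are shown side by side, with no summary of whether response rises across them.

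With about 7 patients per bin, a real but gradual relation could be present and not be visible in the tables. What is at stake is the yield of an exploratory biomarker. The primary result and the sample size are not involved.

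**Working it through.** **1. Sample size, reproduced first.** SAP section 4 states: "Thirty-five patients were required" so that the lower 95% limit can "exceed the 5% threshold in ORR", "with the expected ORR is 25% with a statistical power of 90" percent. With the exact (Clopper-Pearson) interval, 5 of 35 has a lower limit of 4.8% and 6 of 35 has 6.6%, so at least 6 responders are needed. P(X ≥ 6 | n = 35, p = 0.25) = 0.902. The stated 35 and 90% agree.

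**2. Precision per bin.** 35 / 5 = 7 patients per bin on average. Exact 95% limits:

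| Responders | Lower | Upper |
|---|---|---|
| 0 of 7 | 0% | 41.0% |
| 2 of 7 | 3.7% | 71.0% |

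**3. A smooth gradient (assumed).** The SAP gives no CD25 distribution and no relation to response. Assumptions: n = 35; CD25 fraction drawn from Beta(0.6, 1) or Beta(1, 1.5); response logistic in CD25, with ORR 5% at 0% and 55% at 100%. The implied odds ratio per 10 points is exp{[logit(0.55) − logit(0.05)] / 10} = exp{(0.201 + 2.944) / 10} = exp(0.3145) = 1.37. Overall ORR is about 18%. With 4,000 trials per scenario (two-sided 5% level, used only as a yardstick for information):

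| Quantity | Share of trials |
|---|---|
| Five bin ORRs out of order, although the truth is monotone | about 51% to 58% |
| Relation detected by the 20% split (Fisher) | about 5% to 16% |
| Relation detected by the continuous rate (Wilcoxon) | about 42% to 52% |
| Observed direction reversed at the 20% cut | about 5% to 8% |

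The simulation standard error is at most √(0.5 × 0.5 / 4000) = 0.8 percentage points. Repeat runs moved the ends of the ranges by one or two points.

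**4. Other gradients (assumed).** Here overall ORR is the SAP's 25%, CD25 is uniform, spread at 7 per bin, or right-skewed (Beta(0.5, 1.2)), and score tests are used throughout. Power over the three distributions:

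| Odds ratio per 10 points | Continuous rate | Trend over five ordered bins | 20% cut |
|---|---|---|---|
| 1.2 | 24–30% | 14–23% | 5–21% |
| 1.4 | 59–71% | 38–58% | 11–53% |
| 1.6 | 83–91% | 61–82% | 16–76% |

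The continuous rate leads in every row. The ordered bins come second, so using the order alone already recovers part of the loss.

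**5. A step at 20% (assumed).** With ORR 5% below 20% and 35% to 40% above it, and the distributions of step 3, the 20% split detects the relation in about 29% to 58% of trials and the continuous rate in about 25% to 46%. The ranking turns round.

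**The case against.** The strongest reply is that the SAP does what it sets out to do. The stated objective is a preliminary look at biomarkers and a measurement of CD25; no predictive aim is written down. No comparison is planned (5.3.3), so a power figure faults the plan for a test that it never proposes. Both sets of categories are shown with exact intervals, so a reader will see how wide they are. The simulation in step 3 assumes a smooth rise, which suits a continuous analysis, and step 5 shows the opposite ranking under a step. The SAP does not say at what resolution the CD25 rate is recorded. And 5.7 already permits a further exploratory analysis.

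Most of this stands and limits the point. The power figures measure lost information; they do not show a failed test. What does not fall away is that the SAP chose to look at response by CD25, and the specified look ignores both the rate and the order. An analysis added under 5.7 after the data are seen also carries less weight than one written in beforehand.

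Three stronger readings might be inferred and are not supported:

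- **That the bins easily invert a true relation.** Neighbouring bins out of order are not an inverted relation. Direction reverses at the 20% cut in about 5% to 8% of trials in step 3, and a rank analysis of the continuous rate also reverses in some, below 5%. Much of this is due to having 35 patients.
- **That the plan will yield a spurious cut-off.** The 20% cut is pre-specified, and nothing in the SAP proposes choosing one from the results.
- **That the trial fails an aim to show that CD25 predicts benefit.** No such aim is stated.

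**Conclusion.** The point holds as a cheap improvement to an exploratory analysis. The only specified link between tumour CD25 and response is descriptive ORR in five bins of about 7 and at one 20% cut. That discards information and can hide a graded relation: under the assumed gradient, roughly 5% to 16% detection at the cut against 42% to 52% with the continuous rate.

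The size depends on an assumed CD25 distribution, an assumed smooth gradient and a rate recorded as a percentage without error. The advantage is absent if response truly steps at 20%. For a weak relation (odds ratio 1.2 per 10 points) even the continuous analysis would detect only 24% to 30%. The primary ORR analysis and the sample size are untouched.

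**What to change.** In SAP 5.3.4 or 5.4.3, pre-specify one analysis in the overall population, labelled exploratory, that uses the CD25+ rate as recorded. Either of these would do:

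- a dot or box plot of CD25+ rate by responder status, with the ROC area and its 95% CI; or
- a logistic odds ratio for response per 10 percentage points, with 95% CI.

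If the rate is recorded only in categories, use the ordered categories instead. Present the result as an estimate without a test, which keeps it consistent with 5.3.3. Keep both existing category sets as description.

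The cost is one figure and one estimate, with no new data if the rate is recorded as a percentage. The downside is one more exploratory result to report, to be labelled as such in line with 5.7.
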